10.3 Statistical Methodology

10.3.1 Study Design

This is a single-stage phase 2 study evaluating the efficacy of combination ofatumumab and GSK 2110183. The protocol will accrue 31 response-evaluable patients. Patients who have received at least one dose of GSK2110183 will be evaluable for safety and response.

10.3.2 Sample Size, Significance Level and Power

In the pivotal trial of single-agent ofatumumab in fludarabine-refractory CLL which led to FDA approval (Wierda et al, 2010), the overall response rate in the BF-ref cohort which is used as the historical comparator for our current study population, was 47% (0.470). The proposed study will accrue 31 subjects in the sample size to decide whether the proportion responding, P , is less than or equal to 0.470 or greater than or equal to 0.670, a 20% increase in response rate. A 20% increase in response rate is generally considered a clinically significant change. If the number of responses is 19 or more, the hypothesis that $P \leq 0.470$ is rejected with a target error rate (α error) of 0.10 and an actual error rate of 0.079. If the number of responses is 18 or less, the hypothesis that $P \geq 0.670$ is rejected with a target error rate of 0.20 and an actual error rate of 0.192. Therefore, the significance level (i.e., the probability of rejecting H_0 when it is true) is 0.10.

10.3.3 Statistical Analysis

Univariate analysis of response predictors will be performed using Fisher's exact test and Wilcoxon rank-sum test. Response predictors to be evaluated will include age, abnormal baseline serum laboratory values (e.g. LDH, beta-2 microglobulin, albumin, direct antiglobulin test, hemoglobin, lymphocytes, neutrophils, platelets, creatinine, ZAP70, CD38), clinical features (bulky adenopathy, organomegaly, RAI stage), disease status (relapsed or refractory), number of prior lines of therapy (1,2, vs 3 or more), FISH cytogenetics (17p/11q deletion vs none), IgVH status (mutated versus unmutated). Survival will be calculated using the Kaplan-Meier method. Statistical analyses will be applied using SAS 9.2.

10.4 Safety evaluation

Data from all subjects who receive any protocol therapy will be included in the safety analyses. Subjects who entered the study and did not receive any protocol therapy and had this confirmed, will not be evaluated for safety. Severity of adverse events will be graded by NCI Common Terminology criteria version 4.03. SAEs will be reported at a minimum of up to 6 months after the last dose or to the end of the follow-up period whichever is longer. If a subject starts other therapy, then SAEs will

no longer be required to be reported. Note: Causality must be assessed for each study drug separately. SAE forms used must allow for attribution for each study drug to be documented separately. A formal review of safety data after the first 6 patients have completed cycle 1 of the Treatment Phase will be performed before continuing accrual.

10.5 Patient Accrual and Study Duration

Accrual for this study is expected to be about 2 patients per month. Thus, patient accrual is expected to be complete within 18-24 months. Additional time will be required to allow the response data to mature.

All patients registered in the study will be accounted for. The number of patients who die or withdraw before treatment begins will be specified. The distribution of follow-up times will be described and the number of patients lost to follow-up will be given.

11 Regulatory Considerations

11.1 Institutional Review Board/Ethics Committee approval

The protocol for this study has been designed in accordance with the general ethical principles outlined in the Declaration of Helsinki. The review of this protocol by the IRB/EC and the performance of all aspects of the study, including the methods used for obtaining informed consent, must also be in accordance with principles enunciated in the declaration, as well as ICH Guidelines, Tri-Council Policy Statement on Ethical Conduct of Research Involving Humans (TCPS) and Part C Division 5 of the Food and Drug Regulations of Health Canada.

The Investigator will be responsible for preparing documents for submission to the relevant IRB/EC and obtaining written approval for this study. The approval will be obtained prior to the initiation of the study.

The approval for both the protocol and informed consent must specify the date of approval, protocol number and version, or amendment number.

Any amendments to the protocol after receipt of IRB/EC approval must be submitted by the Investigator to the IRB/EC for approval. The Investigator is also responsible for notifying the

IRB/EC of any serious deviations from the protocol, or anything else that may involve added risk to subjects.

Any advertisements used to recruit subjects for the study must be reviewed and approved by the IRB/EC prior to use.

11.2 Informed consent

The Investigator must obtain informed consent of a subject or his/her designee prior to any study related procedures as per GCPs as set forth in the TCPS and ICH guidelines.

Documentation that informed consent occurred prior to the subject's entry into the study and the informed consent process should be recorded in the subject's source documents. The original consent form signed and dated by the subject and by the person consenting the subject prior to the subject's entry into the study, must be maintained in the Investigator's study files.

11.3 Study records requirements

The Investigator must ensure that the records and documents pertaining to the conduct of the study and the distribution of the protocol therapy, that is copies of CRFs or other data collection system and source documents (original documents, data, and records [e.g., hospital records; clinical and office charts; laboratory notes; memoranda; subject's diaries or evaluation checklists; SAE reports, pharmacy dispensing records; recorded data from automated instruments; copies or transcriptions certified after verification as being accurate copies; microfiches; photographic negatives, microfilm, or magnetic media; x-rays; subject files; and records kept at the pharmacy, at the laboratories, and at medico-technical departments involved in the clinical study; documents regarding subject treatment and drug accountability; original signed informed consents, etc.]) be retained by the Investigator for as long as needed to comply with national and international regulations (generally 2 years after discontinuing clinical development or after the last marketing approval). In Canada records relating to clinical trials must be maintained for 30 years. These records must be made available to Health Canada within 2 days if there is a risk to the health of trial subjects, otherwise they must be made available within 7 days of a request from Health Canada.

The Investigator agrees to adhere to the document/records retention procedures by signing the protocol.

Appendix 1: IWCLL Diagnostic Criteria for CLL 2008

(Hallek et al. Blood 2008;111:5446)

The diagnosis of B-CLL must have been made at some point in the past, prior to study entry. **All** of the following criteria must have been satisfied at the time of diagnosis:

- Persistent B lymphocytosis of $\geq 5 \times 10^9/L$ for the duration of at least 3 months. Morphologically, the lymphocytes must appear mature.
- Lymphocyte immunophenotyping shows the presence of B-cell markers CD19, CD20, CD23 with CD5 antigen (and absence of other pan-T cell markers)
- The B cell is monoclonal with regards to kappa or lambda light chain restriction

Greater than 55% prolymphocytes and/or $15 \times 10^9/L$ absolute prolymphocytes in the peripheral blood establishes a diagnosis of prolymphocytic leukemia and would be deemed ineligible for this study.

A bone marrow aspirate/biopsy is not necessary for the diagnosis of B-CLL but if done for diagnostic purposes.

Appendix 2. Drugs potentially affected by GSK2110183***PROHIBITED DRUGS WHILE ON STUDY**

CYP3A Substrate	Therapeutic Area
carbamazepine	Anticonvulsants
ergotamine, dihydroergotamine	Antimigraine
clarithromycin,	Antimicrobials
pimozide	Antipsychotics
amprenavir, atazanavir, indinavir, lopinavir, ritonavir, saquinavir	Antivirals
amiodarone, disopyramide, quinidine, bosentan	Cardiovascular Agents
cyclosporine, everolimus, sirolimus, tacrolimus	Immunosuppressive Agents
OAT1B1 Substrate	Therapeutic Area
casprofugin	Antifungal
atrasentan, methotrexate	Anti-cancer
BCRP Substrate	Therapeutic Area
topotecan	Anti-cancer

USE WITH CAUTION WHILE ON STUDY

CYP3A Substrate	Therapeutic Area
fentanyl,	Analgesics
alfentanil, ropivacaine	Anesthetics
losartan	Angiotensin II Inhibitors
ethosuxamide, trimethadione	Anticonvulsants
buspirone, roboxetine, sertraline, trazadone, venlafaxine	Antidepressants and Anxiolytics
emadastine, loratadine	Antihistamines
artemether, halofantrine, lumefantrine, quinine	Antimalarial
erythromycin, clindamycin, rifabutin, rifampin	Antimicrobials
eletriptan	Antimigraine
□-dihydroergocriptine, bromocriptine	Antiparkinsonians
aripiprazole, bromperidol, clozapine, haloperidol, quetiapine	Antipsychotics
oxybutynin, tolterodine	Antispasmodics
bosentan, delavirdine, tipranavir, nelfinavir, amprenavir, atazanavir, delaviridine, efavirenz, fosamprenavir, indinavir, lopinavir, nelfinavir, nevirapine, ritonavir, saquinavir	Antivirals
amlodipine, barnidipine, diltiazem, dofetilide, eplerenone, felodipine, nifedipine, pranidipine, propafenone, verapamil, vesnarinone	Cardiovascular Agents
sildenafil, tadalafil, vardenafil	Erectile dysfunction treatments
aprepitant, lansoprazole	Gastrointestinal Agents
atorvastatin, lovastatin, simvastatin	HMG CoA reductase inhibitors
alprazolam, chlordiazepoxide, diazepam, flunitrazepam, midazolam, propofol, triazolam, zolpidem, zopiclone	Hypnotics and Sedatives

Appendix 2. Drugs potentially affected by GSK2110183***PROHIBITED DRUGS WHILE ON STUDY**

CYP3A Substrate	Therapeutic Area
carbamazepine	Anticonvulsants
ergotamine, dihydroergotamine	Antimigraine
clarithromycin,	Antimicrobials
pimozide	Antipsychotics
amprenavir, atazanavir, indinavir, lopinavir, ritonavir, saquinavir	Antivirals
amiodarone, disopyramide, quinidine, bosentan	Cardiovascular Agents
cyclosporine, everolimus, sirolimus, tacrolimus	Immunosuppressive Agents
OAT1B1 Substrate	Therapeutic Area
casprofugin	Antifungal
atrasentan, methotrexate	Anti-cancer
BCRP Substrate	Therapeutic Area
topotecan	Anti-cancer

USE WITH CAUTION WHILE ON STUDY

CYP3A Substrate	Therapeutic Area
fentanyl,	Analgesics
alfentanil, ropivacaine	Anesthetics
losartan	Angiotensin II Inhibitors
ethosuxamide, trimethadione	Anticonvulsants
buspirone, roboxetine, sertraline, trazadone, venlafaxine	Antidepressants and Anxiolytics
emadastine, loratadine	Antihistamines
artemether, halofantrine, lumefantrine, quinine	Antimalarial
erythromycin, clindamycin, rifabutin, rifampin	Antimicrobials
eletriptan	Antimigraine
□-dihydroergocriptine, bromocriptine	Antiparkinsonians
aripiprazole, bromperidol, clozapine, haloperidol, quetiapine	Antipsychotics
oxybutynin, tolterodine	Antispasmodics
bosentan, delavirdine, tipranavir, nelfinavir, amprenavir, atazanavir, delaviridine, efavirenz, fosamprenavir, indinavir, lopinavir, nelfinavir, nevirapine, ritonavir, saquinavir	Antivirals
amlodipine, barnidipine, diltiazem, dofetilide, eplerenone, felodipine, nifedipine, pranidipine, propafenone, verapamil, vesnarinone	Cardiovascular Agents
sildenafil, tadalafil, vardenafil	Erectile dysfunction treatments
aprepitant, lansoprazole	Gastrointestinal Agents
atorvastatin, lovastatin, simvastatin	HMG CoA reductase inhibitors
alprazolam, chlordiazepoxide, diazepam, flunitrazepam, midazolam, propofol, triazolam, zolpidem, zopiclone	Hypnotics and Sedatives

CYP3A Substrate	Therapeutic Area
pioglitazone, repaglinide, rosiglitazone	Hypoglycemic Agents
temsirolimus	Immunosuppressive Agents
tretinoin	Retanoids
CYP2C8 Substrate	Therapeutic Area
repaglinide	Hypoglycemic Agents
OATP Substrate	Therapeutic Area
atorvastatin, cerovastatom, fluvastatin, pravastatin, simvastatin, rosuvastatin	HMG CoA reductase inhibitors ²

1. Please note some drugs may be listed more than once. This is due to the fact that they are substrates for both CYP and a transporter (e.g., OATP1B1, BCRP).
2. If patients are on a high dose of a HMG CoA reductase inhibitor, dose reduction should be considered. Monitoring for toxicities (such as rhabdomyolysis) should be considered.

USE WITH CAUTION WHILE ON STUDY

Other Drugs that could affect GSK2110183	Therapeutic Area
quinidine	Antiarrhythmics
fluvoxamine, fluoxetine, nefazodone, paroxetine	Antidepressants
fluconazole, itraconazole, ketoconazole, terbinafine, voriconazole	Antifungals
ciprofloxacin, clarithromycin, erythromycin, isoniazid, rifamycin class agents (e.g., rifampin, rifabutin, rifapentine), telithromycin, troleandomycin	Anti-infectives
amprenavir, atazanavir, delaviridine, efavirenz, fosamprenavir, indinavir, lopinavir, nelfinavir, nevirapine, ritonavir, saquinavir	Antivirals
phenobarbital, oxandrolone, tizanidine, gemfibrozil	Miscellaneous

* A copy of this information to be given to the study participants.

Appendix 3 – ECOG Performance Status Scale

SCORE	DESCRIPTION
0	Fully active, able to carry on all pre-disease performance without restriction.
1	Restricted in physically strenuous activity but ambulatory and able to carry out work of a light or sedentary nature, e.g., light house work, office work.
2	Ambulatory and capable of all self-care but unable to carry out any work activities. Up and about more than 50% of waking hours.
3	Capable of only limited self-care, confined to bed or chair more than 50% of waking hours.
4	Completely disabled. Cannot carry on any self-care. Totally confined to bed or chair.
5	Dead.

Appendix 4 - NCI CTC Version 4.03

TOXICITY WILL BE SCORED USING NCI CTC VERSION 4.03 FOR TOXICITY AND ADVERSE EVENT REPORTING. A COPY OF THE NCI CTC VERSION 4.03 CAN BE DOWNLOADED FROM THE CTEP HOMEPAGE: ([HTTP://CTEP.INFO.NIH.GOV](http://CTEP.INFO.NIH.GOV)).
ALL APPROPRIATE TREATMENT AREAS HAVE ACCESS TO A COPY OF THE CTC VERSION

Appendix 5 - IWCLL Response Criteria 2008 - Hallek. Blood 2008;111:5446**Complete Remission (CR)**

CR requires all of the following criteria to be met for a period of at least 2 months after completion of therapy:

- a) Peripheral blood lymphocytes $< 4 \times 10^9/L$
- b) Absence of significant lymphadenopathy ($>1.5\text{cm}$) by physical exam and appropriate radiology
- c) No hepatomegaly or splenomegaly by physical exam and appropriate radiology
- d) Absence of constitutional symptoms
- e) Normal CBC as exhibited by:
 - Neutrophils $> 1.5 \times 10^9/L$ without need for exogenous growth factors
 - Platelets $>100 \times 10^9/L$ without need for platelet transfusion or exogenous growth factors
 - Hemoglobin $> 110\text{g/L}$ (untransfused and without need for exogenous erythropoietin)
- f) Bone marrow to be done at least 2 months after the last treatment and if clinical and laboratory results (first 5 points under “Complete Remission”) demonstrate that a CR has been achieved. The marrow sample must be at least normoceleular for age, with $<30\%$ of nucleated cells being lymphocytes. Lymphoid nodules should be absent. If marrow is hypocellular, a repeat sample should be taken after 4 weeks or when peripheral blood counts have recovered.

Complete Remission with incomplete bone marrow recovery (CRi)

This category describes patients who fulfill all the criteria for CR (including the marrow examinations) but who have persistent anemia or thrombocytopenia or neutropenia apparently unrelated to disease activity but related to drug toxicity.

Partial Remission (PR)

PR requires all the following criteria to be met for a period of at least 2 months:

- a) $\geq 50\%$ decrease in the peripheral blood lymphocytes from pre-treatment value
- b) $\geq 50\%$ reduction in the sum products of up to 6 lymph nodes, or in one lymph node diameter if only a single lymph node was present before therapy. To be determined by physical exam or CT scan (if abnormal at baseline)
- c) No increase in any lymph node and no new enlarged node. In small lymph nodes (<2 cm), an increase of <25% is not considered to be significant.
- d) $\geq 50\%$ reduction in hepatomegaly and/or splenomegaly by physical exam or on CT scan (if abnormal at baseline)

In addition, one or more of the following must be present for at least 2 months:

- e) Neutrophils $\geq 1.5 \times 10^9/L$ without need for exogenous growth factor support
- f) Platelets $> 100 \times 10^9/L$ or 50% improvement over baseline without need for exogenous growth factors
- g) Hemoglobin $> 110 \text{ g/L}$ or 50% improvement over baseline (without transfusions or erythropoietin support)

Stable Disease (SD)

Not CR, PR or PD (equivalent to nonresponse)

Progressive Disease (PD)

At least one of the following:

- a) Lymphadenopathy (any one event):
 - a. Appearance of any new lesion, such as enlarged lymph nodes ($>1.5\text{cm}$), splenomegaly, hepatomegaly or other organ infiltrates)
 - b. An increase by $\geq 50\%$ in greatest determined diameter of any previous site
 - c. A lymph node of 1 to 1.5cm must increase by 50% or more to a size greater than 1.5cm in the longest axis. A lymph node of more than 1.5cm must increase to more than 2.0cm in the longest axis

- b) $\geq 50\%$ increase in the size of the liver and/or spleen as determined by measurement below the costal margin or appearance of palpable hepatomegaly or splenomegaly not previously present
- c) $\geq 50\%$ increase in the absolute number of circulating lymphocytes with at least $5.0 \times 10^9/L$
- d) Transformation to a more aggressive histology (eg Richter's syndrome or prolymphocytic leukemia with $>55\%$ prolymphocytes).
- e) Occurrence of cytopenias (neutropenia, anemia, or thrombocytopenia) attributable to CLL.
 - a. During therapy: cytopenias cannot be used to define PD
 - b. After therapy: The progression of any cytopenia (unrelated to autoimmune cytopenia), as documented by a decrease of Hb levels by more than 20g/L or to $<100g/L$, or by a decrease of platelet counts by $>50\%$ or to less than $100 \times 10^9/L$, which occurs at least 3 months after treatment, if the marrow biopsy demonstrates an infiltrate of clonal CLL cells.

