4.2 Endpoints

4.2.1 Primary Endpoint

- Overall response rate (includes partial and complete responses)

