5.2 Screening and Eligibility

The Investigator or designee is responsible for keeping a record of all subjects who sign an Informed Consent Form for entry into the study. All subjects will be screened for eligibility. Screening procedures are outlined in Section 2, Schedule of Study Assessments and must take place within 28 days prior to initiation of therapy.

Approximately 31 subjects with relapsed or refractory CLL will be screened for enrollment and must meet the eligibility criteria below.

Subjects must meet the following inclusion/exclusion criteria to be eligible for the study.

Inclusion criteria

Patients must fulfil all of the following criteria to be eligible for admission to the study:

- A confirmed diagnosis of B-cell CLL by IWCLL 2008 criteria (Appendix 1)
- Patients must have evidence of disease progression as evidenced by rapid doubling of peripheral lymphocyte count, progressive lymphadenopathy or hepatosplenomegaly, worsening anemia or thrombocytopenia, or progressive constitutional symptoms [including fatigue, weight loss, night sweats, fever (without infection)]
- Must be relapsed or refractory to at least one prior fludarabine-containing regimen (no maximum number of prior regimens).
- Age \geq 18 years.
- ECOG performance status of 0, 1 or 2 (Appendix 3)
- Signed the Informed Consent form
- Life expectancy of \geq 6 months
- Able to swallow and retain oral medication
- Normal HbA1C \leq 0.07
- Fasting blood sugar $<$ 7mmol/L

Exclusion criteria:

Subjects meeting any of the following criteria are excluded from this study:

- CLL therapy, including stem cell transplantation, within 4 weeks of study initiation. Corticosteroids alone may be administered up to seven days prior to the first dose of study drug.
- Treatment with any known non-marketed drug substance or experimental therapy within 5 terminal half-lives or 4 weeks prior to enrollment, whichever is longer, or currently participating in any other interventional clinical study
- Prior treatment with anti-CD20 monoclonal antibody or alemtuzumab within 3 months prior to start of therapy
- Known hypersensitivity to ofatumumab, GSK2110183, or any components therein.
- Anticoagulants are permitted only if the subject meets PTT and INR entry criteria while on anticoagulants (INR and PTT ≤ 1.5 times upper normal limit). Their use must be monitored in accordance with local institutional practice.

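### The lymphocyte criterion for partial remission is mandatory and has no baseline qualifier, so a nodal responder with a normal starting count can be scored as stable disease in the primary endpoint

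*Combined protocol and SAP*

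**What the plan says.** The primary endpoint (Section 4.2.1) is the response rate, CR plus PR. Section 7 has it scored by Appendix 5.

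For PR, Appendix 5 says "PR requires all the following criteria to be met for a period of at least 2 months" and lists four items:

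- **a:** at least a 50% "decrease in the peripheral blood lymphocytes from pre-treatment value". There is no condition on the baseline count and no absolute alternative.
- **b:** at least a 50% node reduction, with the note "To be determined by physical exam or CT scan (if abnormal at baseline").
- **c:** no node growth and no new enlarged node.
- **d:** at least a 50% "reduction in hepatomegaly and/or splenomegaly by physical exam or on CT scan (if abnormal at baseline").

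At least one of three blood-count items (e to g) must also hold. Stable disease is the residual class: "Not CR, PR or PD (equivalent to nonresponse").

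On entry, Appendix 1 says "The diagnosis of B-CLL must have been made at some point in the past, prior to study entry", and the lymphocytosis of at least 5 x 10^9/L has to have been present at that diagnosis. Section 5.2 asks for evidence of progression from a list of alternatives: rapid lymphocyte doubling, "progressive lymphadenopathy or hepatosplenomegaly, worsening anemia or thrombocytopenia, or progressive constitutional symptoms". Sections 10.2 and 10.3.1 make every patient given at least one dose of GSK2110183 evaluable for response.

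**The concern.** A patient may enter on nodal progression alone, with a lymphocyte count in the normal range. Criterion a then asks for a normal count to halve. If it does not, PR is unavailable however far the nodes shrink. Unless the patient reaches CR, the result is stable disease, and the patient stays in the denominator.

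The rule is also out of step with CR, which uses an absolute lymphocyte limit (below 4 x 10^9/L). The same patient can satisfy the lymphocyte item for the better response category and fail it for the lesser one.

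The stake is the primary endpoint of a single-arm trial decided on a count of 19 out of 31. Some responses could be lost for a reason unrelated to drug effect. Alternatively, if readers waive criterion a informally, the count depends on a rule the protocol does not contain, in an open-label trial at one institution.

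**Working it through.** **1. The plan's own figures.** Section 10.3.2 gives N = 31, success at 19 or more responses, a null rate of 0.470 and an alternative of 0.670, with actual error rates of 0.079 and 0.192.

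- P(Bin(31, 0.47) ≥ 19) = 0.0786, which agrees with 0.079.
- P(Bin(31, 0.67) ≥ 19) = 0.8085, so the type II error is 1 − 0.8085 = 0.1915, which agrees with 0.192.

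The design arithmetic is sound. The response definition does not enter it.

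**2. One patient taken through Appendix 5 (illustrative values).** Nodal relapse, baseline lymphocytes 1.5 x 10^9/L, no organomegaly. On treatment the nodes shrink by 80%, the largest remains above 1.5 cm, and lymphocytes are 1.2 x 10^9/L. Assume c and at least one of e to g hold.

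| Item | Result |
|---|---|
| PR a: lymphocyte fall ≥ 50% | (1.5 − 1.2)/1.5 = 20%: not met |
| PR b: node reduction ≥ 50% | 80%: met |
| PR d: liver/spleen | nothing to reduce; waived if the qualifier covers the criterion |
| CR lymphocyte limit < 4 x 10^9/L | 1.2: met, and met at baseline |
| CR node limit | not met |
| Category as written | stable disease |

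Criterion a alone is enough to produce this result, whichever way d is read.

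**3. Size, as a worst case.** The documents do not give the number of affected patients, k. Suppose k of the 31 could never be scored as responders and the other 31 − k respond at the true rate p. The chance of declaring success is P(Bin(31 − k, p) ≥ 19).

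| k (assumed) | p = 0.67 | p = 0.47 |
|---|---|---|
| 0 | 0.808 | 0.079 |
| 1 | 0.737 | 0.054 |
| 2 | 0.650 | 0.035 |
| 3 | 0.551 | 0.021 |

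**4. A softer assumption.** A normal count can still halve on treatment, and CR stays open. If the k patients respond at half the rate (0.67/2 = 0.335), the number of responses is Bin(31 − k, 0.67) + Bin(k, 0.335). The chance of 19 or more is then 0.773 at k = 1 and 0.690 at k = 3. The half rate is an illustration and is not taken from the documents.

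**The case against.** The best counter-argument is that affected patients are not shut out. A normal count may fall by half, and CR needs no percentage fall. That stands, and it is why the table in step 3 is only a worst case. It does not remove the gap: CR also needs no node above 1.5 cm, adequate blood counts and a marrow examination at least 2 months after the last treatment, so a partial nodal responder will not usually get there.

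A reader might go further and infer that any patient without organomegaly can never be PR, because the qualifier in d follows the mention of CT and may describe only the method. Section 2, note 3, which ties rescanning to abnormalities on the baseline CT, gives that reading some support. The documents do not bear it out as the main reading. Criterion d speaks of reducing an enlargement, which presupposes one, and Section 10.3.3 plans to test organomegaly as a predictor of response, which would make little sense if patients without it could not achieve PR. The scope of the qualifier needs clarifying, but it should not be counted as a second defect of the same weight.

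Nor do the documents support a claim that marrow responders are lost, since PR contains no marrow item.

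Two further objections stand. The strict rule also lowers the false-positive risk, as the right-hand column in step 3 shows. And the documents do not show how the trial behind the 47% comparator scored patients with a normal baseline count, so the direction of any net bias against that figure cannot be stated.

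**Conclusion.** The point holds for criterion a. It is mandatory, it lacks the qualifier found in b and d, and the entry criteria admit patients to whom it does not sensibly apply. Following the text can put a clear partial nodal responder among the non-responders of the primary endpoint.

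Its size is unknown. In the worst case a single affected patient takes power from 0.808 to 0.737, below the 80% implied by the target error rate of 0.20, and three take it to 0.551; with half-rate responders the figures are 0.773 and 0.690. All of these rest on an assumed k. They show how little slack the cut-off of 19 leaves and are not an estimate of the loss. A conclusion that the trial is biased against the combination relative to 47% is not supported.

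**What to change.** Amend the PR section of Appendix 5 before responses are scored:

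1. Apply the 50% fall in criterion a only when the baseline lymphocyte count is raised, for example at or above the protocol's own CR limit of 4 x 10^9/L. Otherwise require the count to stay below that limit.
2. State that the baseline qualifier in b and d applies to the criterion itself and not only to the CT method.
3. Require at least one of a, b or d to be abnormal at baseline for PR to be assessable. Keep patients with none abnormal in the denominator as non-responders unless they meet CR.
4. Report the response rate under the literal rule as a sensitivity analysis.

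N = 31 and the cut-off of 19 do not change. The cost is a few words: screening already collects hematology, node and liver/spleen measurements and CT (Section 2), so the criteria that apply to each patient can be derived from existing data. There are two downsides. Patients are judged on different numbers of criteria, and the amended rule may be more lenient than the one behind the 47% comparator. Item 4 shows how far the result depends on that choice.
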